- Detailed description of the deviation (including which data is affected by the deviation);
- Date of decision;
- People involved in the decision, with signature.

8.1 Description of the deviations from the SAP

1. Standard deviation (SD) of the glucose value

- a. Rationale: SD of the glucose value was included as variable because of its added value to indicate glycemic variability.
- b. Detailed description: the SD of the glucose value was added as parameter considering it is a commonly used parameter besides the coefficient of variation and interquartile range of the glucose value to indicate glycemic variability. The SD was calculated for day time, night time and the combination. No data were affected by the addition of this parameter.
- c. Date of decision: May 1, 2023.
- d. People involved in the decision (with signature): [name], [name] and [name].

2. Time below range (TBR) and time above range (TAR)

- a. Rationale: level 1 and level 2 for the TBR and TAR were included in order to report all the important glycemic metrics, following the International Consensus guidelines.
- b. Detailed description: according to the SAP, only the TBR and TAR in total should be calculated (not as separate levels). In addition to the total TBR and TAR, also level 1 and 2 of the TBR and TAR were calculated. These are essential parameters to indicate glycemic control, following the International guidelines on how to report glycemic metrics (Battelino *et al*, Lancet Diabetes Endocrinol (2023)). These metrics were calculated for day time, night time and the combination. These additional parameters had no effect on the data.

Revision	D02	Document number:	SAP
	Document title:	FAST-1	
	Status:	APPROVED	
	TPL 013.D02	This document is uncontrolled when printed	

- c. Date of decision: May 1, 2023.
- d. People involved in decision (with signature): [name], [name] and [name].

3. Exclusion of AP data acquired for five participants

a. Rationale:

A critical procedural error was discovered in the process of data analysis, which led to invalidity of a part of the FCL data. FCL data from the Lyumjev-Humalog sequence (n=5) had to be excluded. Other data from this sequence could still be included (e.g., adverse events). To mention that all FCL data from the Humalog-Lyumjev sequence (n=7) were included.

b. Details on deviation:

Humalog is used as default insulin in the Inreda AP, and study participants who were randomized to the Humalog-Lyumjev sequence already had their settings optimized for Humalog by the diabetes care team over a long period, considering AP treatment was their regular care at the time. However, in case study participants were randomized to the Lyumjev-Humalog sequence, their settings needed optimization to match with the characteristics of the ultra-rapid insulin Lyumjev. For these participants, the settings of their insulin curve and preinjection were adjusted to take the faster and shorter insulin action into account. These substantial adjustments of the insulin settings during Lyumjev use were not changed back to the Humalog settings that equaled the settings before the start of the study. The Lyumjev-specific Inreda AP settings that were still used after switching back to Humalog affected the glucose regulation of these participants. Therefore, the true impact on glycemic control comparing the insulins within that sequence could not be studied correctly and would have led to invalid outcomes derived from the FCL data. The FCL data obtained in the Lyumjev-Humalog sequence could therefore not be used as valid study data. Only FCL data from the Humalog-Lyumjev sequence were included to determine the outcome parameters (7 of the 12 participants), whereas FCL data from the Lyumjev-Humalog sequence were excluded from further data analysis (5 of 12 participants).

c. Date of decision:

May 4, 2023.

- d. People involved in decision (with signature): [name], [name] and [name].

8.2 Signatures of the people involved in the decisions:

Name (function): [name] (Data specialist)

Signature: 

Name (function): [name] (Lead Clinical Operations)

Signature: 

Name (function): [name] (Clinical project manager)

Signature: 

Revision	D02	Document number:	SAP
	Document title:	FAST-1	
	Status:	APPROVED	
	TPL 013.D02	This document is uncontrolled when printed	

9 Revision History

Rev	Author	Change description	Reviewed by	Approved by	Date
D01	[name]	New document	[name]	[name]	29-08-2022
D02	[name]	Addition of SAP deviations and signatures of people involved	[name]	[name]	01-07-2025

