8.3 Study procedures

The study starts with informing the patients about the study. If patients want to participate the informed consent form will be signed first and thereafter the patients will be screened, which can be performed online or in the CRC. The study will be performed at home and subjects can live according to their own daily routine.

At the start of the first study period the subject will receive the insulin cartridges for the first study period. After the first 30 days, there will be a washout period of 8 days where subjects will use Humalog. After the wash-out period the subjects will receive the second insulin formulation according to randomization. The same procedure as written above will be repeated. During the study conduct there will be four additional visits by the investigator: at the start and end of both the intervention and control period.

If adverse events occur during the study, the subject has to contact the investigator. If desired, an unscheduled visit could take place. If a device deficiency occurs during the study, the subject has to contact the investigator only if this is insulin-related. If there are other technical problems, the patient should follow the regular treatment protocol and contact the customer service of Inreda Diabetic B.V.

During both study periods subjects are asked to keep a Wi-Fi access point with them so researchers can assess the data if necessary. No active real-time monitoring will be performed during the study, the standard monitoring protocol will be complied. This includes monthly portal assessments and assessments at the request of the customer service.

At the start of the study the self-learning algorithm status (on or off) will not be changed. This means that the self-learning algorithm is turned on or off depending on the setting prior to the study.

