5.1.1 CRF Dataset

The CRF data will be collected with an eCRF implemented in *MyResearchManager*. The following data will be collected with the CRF:

- In- and exclusion criteria;
- Gold/Clarke questionnaire;
- Date of informed consent;
- Demography;
- Weight, length, HbA1c;
- Medical history;
- Randomization results;
- Visits information (including telephone contact, decided 'actions' and rationale);
- Concomitant medication;
- Adverse events;
- Device deficiencies;
- Adjustment of AP settings;
- End of study.

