5.3 Standard analysis

The distribution of each parameter (primary, secondary and other study parameters) will be assessed with a histogram and/or q-q plot. For the parameters that are being compared with dependent/paired tests, the distribution of the difference between the groups will be assessed. Based on these assessments, the decision for using data transformations and parametric or nonparametric descriptive analysis and statistical testing will be made for each (group of) parameter(s).

Subsequently, carry-over and period effects will be assessed because of the cross-over design of the study. For each parameter that will be compared between open loop and closed loop, the two randomization groups are first compared using two unpaired t-tests or Mann-Whitney U-tests:

- Sum of open loop and closed loop result (carry-over);
- Difference between the open loop and closed loop result (period).

If a significant difference is found in one of these tests, a carry-over/period effect is present. In that case, the results for that parameter of the second study period cannot be used for the analysis (to estimate the treatment effect) and paired testing will not be possible.

For all statistical tests described in this chapter, a p-value ≤ 0.05 is defined to indicate statistical significance. Descriptive analyses will be performed on the subjects presented in 5.3.3.

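### SAP 8.1 item 3 discards both periods of the Lyumjev-Humalog sequence for an error that acted only after period 1, leaving no randomised closed-loop comparison and confounding insulin with period

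*SAP*

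**What the plan says.** The trial is a two-period, two-sequence cross-over in which the order of the insulins is randomised (Protocol 3; SAP 4). Protocol 8.3 sets the timing: "After the first 30 days, there will be a washout period of 8 days where subjects will use Humalog", and the second insulin follows. Protocol 10 promises that carry-over and period effects will be assessed for every parameter. SAP 5.3 does this by comparing the two randomisation groups. If either effect is found, "the results for that parameter of the second study period cannot be used for the analysis", and paired testing is abandoned.

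SAP 8.1 item 3, decided on May 4, 2023 after an error came to light during data analysis, states that "FCL data from the Lyumjev-Humalog sequence (n=5) had to be excluded". The cause is given as follows: "The Lyumjev-specific Inreda AP settings that were still used after switching back to Humalog affected the glucose regulation of these participants". The reason for exclusion is that "the true impact on glycemic control comparing the insulins within that sequence could not be studied correctly". The consequence is then stated: "Only FCL data from the Humalog-Lyumjev sequence were included to determine the outcome parameters (7 of the 12 participants"). Other data from the excluded sequence, such as adverse events, are kept.

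SAP section 8 requires each deviation entry to contain a "Detailed description of the deviation (including which data is affected by the deviation"). Item 3 identifies the data by sequence and does not separate the two periods.

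**The concern.** The exclusion is wider than the reason given for it. Settings left over from Lyumjev can distort only what was recorded after the return to Humalog. That spoils the five patients' Humalog period, and so their paired difference. It does not spoil their Lyumjev measurements in period 1, and item 3 reports nothing wrong with those.

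Dropping them has a structural cost. Once only one order is left, nothing randomised remains in the closed-loop data. Everyone analysed had Humalog in period 1 and Lyumjev in period 2, so a seasonal change, a learning effect, a study effect or continued tuning of the device counts in full as an insulin effect. The period and carry-over checks need two sequences and cannot be run. Item 3 mentions none of this. A reader could take a before-after comparison in 7 patients for the result of a randomised cross-over.

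The documents also do not say whether settings were adjusted for Lyumjev in period 2 of the 7 retained patients.

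**Working it through.** **Inputs.** Protocol 4.4 and SAP 3: means 12.8 and 9.675 (difference 3.125 points), SD 3.3 in each condition, correlation 0.70, alpha 0.05, power 0.90. SAP 8.1: 7 patients in Humalog-Lyumjev (HL), 5 in Lyumjev-Humalog (LH). The documents give no period effect, so the drifts below are assumptions.

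**The plan's own figure.** SD of the paired difference = 3.3 × √(2 × (1 − 0.70)) = 2.556. Standardised effect = 3.125 / 2.556 = 1.2225. The noncentral t distribution, two-sided 0.05, gives power 0.893 at n = 9 and 0.929 at n = 10. The stated 10 reproduces, as a two-sided test against zero.

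**What each sequence estimates.** Let τ be Lyumjev minus Humalog and π be period 2 minus period 1.

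- HL: mean of Lyumjev minus Humalog = τ + π
- LH: mean of Lyumjev minus Humalog = τ − π
- Both sequences, averaged: τ
- HL alone: τ + π, with no means of separating the two

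**Paired analysis of the 7.** SE = 2.556 / √7 = 0.966. The 95% half-width = 2.447 × 0.966 = 2.36 points. Power for 3.125 against zero is 0.77, and only if π = 0.

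**Effect of a drift favouring period 2 (n = 7, correlation 0.70).**

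| Assumed drift (points) | Two-sided test against zero (Protocol 10.1), no insulin effect | Margin test (SAP 5.3.1), no insulin effect | Margin test, true effect exactly −3.125 |
|---|---|---|---|
| 0 | 5% | – | 5% |
| 0.5 | 7% | – | 12% |
| 1 | 14% | 0.01% | 23% |
| 2 | 41% | 0.4% | 57% |

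The margin test is taken as one-sided 0.05, which is an assumption. In the test against zero, drifts of 1 and 2 points give 10.5% and 27% if the correlation is 0.5, and 33% and 85% if it is 0.9. Under either test the estimate is biased by the full drift, whatever its size.

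**Randomised comparison in period 1 (7 Humalog, 5 Lyumjev).** SE = 3.3 × √(1/7 + 1/5) = 1.932. The 95% half-width = 2.228 × 1.932 = 4.31 points. Two-sided power for 3.125 is 0.31.

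**All unaffected data together.** There are 12 period 1 values and 7 period 2 values. They fall into three cells (Humalog in period 1, Lyumjev in period 1, Lyumjev in period 2) and the model has three mean parameters (baseline, τ, π). The period 2 values are used up in estimating π. A generalised least squares fit at correlation 0.70 accordingly gives an SE for τ of 1.932, the same as period 1 alone. The smaller 0.966 is bought entirely by setting π to zero.

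**Paired analysis of all 12.** If the leftover settings shifted LH Humalog time above range by d, the period-adjusted estimate (the average of the two sequence means) is off by d/2, and the plain mean of 12 differences by 5d/12. Restoring the spoiled period is therefore no remedy.

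**The case against.** The best reply is that much of the damage comes from the error itself. The LH Humalog period is spoiled, so those 5 patients could not enter the planned paired test, and the planned period and carry-over checks would be unsound even with their period 1 data retained. That is right. What the exclusion itself takes away is the period 1 comparison. But that is the only randomised comparison of unaffected closed-loop data.

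A second objection is that silence about period 1 does not prove it sound. Item 3 says settings were adjusted during Lyumjev use but not when, so they may not have been stable after the five training days. This stands as a limit: the claim rests on the SAP's own account, and the settings records should be checked. The reason actually written down does not reach period 1.

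Third, the period 1 comparison is weak. Its half-width exceeds the 3.125 target, SAP 5.3 does not prescribe it for a procedural error, and it sets long-optimised Humalog settings against newly adjusted Lyumjev settings. All true, and to be stated. Imprecision is visible in a confidence interval; confounding is not.

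Fourth, the drifts are illustrative, and with no insulin effect the margin test almost never rejects. That is also correct. The bias by the full drift needs no assumed size.

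Finally, item 3 does name the excluded sequence and the data kept, and Protocol 10 already requires a post hoc statement in the clinical investigation report. That report is not among the documents, so how the result was labelled there is unknown. Item 3 itself is silent on lost randomisation and on period.

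**Conclusion.** The concern holds. The stated reason supports excluding the five patients' data after the switch back to Humalog; it does not support excluding their period 1 data. As written, the primary outcome and every other closed-loop outcome come from a before-after comparison in 7 patients, biased by the whole of any period effect, with no check of that effect possible. Adverse events are outside this point, since both sequences are kept for them.

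The size of the bias is unknown because no period effect is given. The numerical results rest on the plan's SD and correlation, and the rejection rates on assumed drifts as well. The confounding rests on neither. It must be corrected in the record and the reporting, because it changes what the trial can conclude about the two insulins.

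**What to change.** Add a dated addendum to SAP 8.1 item 3 that does the following.

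1. From the CRF item "Adjustment of AP settings" (SAP 5.1.1), list whether and when settings were changed in each period of both sequences, including period 2 of the 7 retained patients. Do this first, since it tests the premise that period 1 is unaffected. If there is another reason to distrust those data, state it.
2. Limit the exclusion to the five LH patients' data after the switch back to Humalog.
3. Report the period 1 difference (7 Humalog, 5 Lyumjev, training days excluded) with its 95% CI, named as the only randomised comparison of unaffected closed-loop data. This follows the logic of SAP 5.3, which gives up only the second period, although SAP 5.3 does not prescribe it for this situation.
4. Label the 7-patient paired result as post hoc and before-after, with insulin confounded with period.
5. Do not offer a paired analysis of all 12 as support.

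The cost is one analysis, one listing and one addendum, all from data already held. The drawback is an estimate with a half-width of about 4.3 points that is unlikely to be conclusive, and whose two arms differ in how long their settings had been optimised. Both limits should be stated beside it.

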3. STUDY DESIGN

Design:

This study is a multicenter, open-label, randomized, cross-over trial which will be performed in a free-living environment.

Duration:

[figure not shown]
The duration of the study per subject is 68 days. During the first thirty days the subject will be randomized to receive the first kind of insulin. After a wash-out period of eight days, the subject will receive the second kind of insulin for another thirty days according to the randomization. The following insulin formulations will be used: Lyumjev 100 units/ml in a 3 ml cartridge and Humalog 100 units/ml in a 3 ml cartridge as standard use of care.

Setting:

This study will be performed at home and patients can live according to their own daily routine. There are two study periods. Each study period lasts thirty days. The first five days of both study periods consist of a training period, which enables the investigator to optimize the settings of the Inreda AP system.

At the beginning of a study period the patient will receive the insulin cartridges according to the randomization. A wash-out period of eight days is included between the two study periods. Subjects will use Humalog during this period, as this is the standard care with the AP. Figure 3.1 shows the flow chart of the study design. During the study conduct there will be four study visits by the investigator: at the beginning and end of the intervention and control period. The training period is included to optimize the settings of the AP if necessary. This data will not be included in the analysis.

Figure 3.1 Flow chart of the study design

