6.4 Summary of known and potential risks and benefits

See chapter 13 for the complete text.

There are no major risks associated with this study. The subjects will use their usual kind of diabetes therapy, in which only the type of insulin is adjusted for thirty days. The most prominent risk is potential altered effectiveness of Lyumjev compared to the currently used insulin, which could lead to hypo- and hyperglycemia, but high and low glucose values will be indicated by alarms given by the AP system.

The individual benefit for the participating patients could be an improved glycemic control during the study.

The burden of the study is relatively low. The participants have to visit the CRC at most 2 times. Besides, the only additional burden for participants is to keep a Wi-Fi access point with them during both study periods.

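### SAP 8.1 item 3 rejects five participants' glucose data because of a settings error but keeps their adverse events without separating those that arose under the error

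*SAP*

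**What the plan says.** SAP 8.1 item 3 records an error found during data analysis. Participants who took Lyumjev first had their pump settings adapted to the faster insulin. "These substantial adjustments of the insulin settings during Lyumjev use were not changed back to the Humalog settings" that had applied before the study. The SAP states the consequence plainly: "The Lyumjev-specific Inreda AP settings that were still used after switching back to Humalog affected the glucose regulation of these participants".

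Two decisions follow. The glucose data are dropped: "FCL data from the Lyumjev-Humalog sequence (n=5) had to be excluded", while "all FCL data from the Humalog-Lyumjev sequence (n=7) were included". The exclusion covers both periods of the affected sequence. Adverse events are treated differently: "Other data from this sequence could still be included (e.g., adverse events".

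Three other places bear on this:

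- Protocol section 2 makes safety a secondary objective. Section 6.4 names the main hazard: "The most prominent risk is potential altered effectiveness of Lyumjev compared to the currently used insulin, which could lead to hypo- and hyperglycemia".
- Protocol section 3 places an eight-day wash-out between the periods: "Subjects will use Humalog during this period, as this is the standard care with the AP". Item 3 does not say whether the Lyumjev settings were already running then, and it gives no date on which they were reset.
- SAP section 8 requires each deviation to describe which data it affects. Item 3 does this for the glucose data only.

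**The concern.** Hypo- and hyperglycaemia are what disturbed glucose regulation looks like to the participant. If the settings error makes the glucose trace unfit as a measure of Humalog, glycaemic adverse events from the same days are unfit as a measure of Humalog for the same reason. Item 3 applies that reasoning to one data source and not to the other, and gives no rule for assigning the events to insulin, period or settings.

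What is at stake is the safety reading. Side effects of Lyumjev are naturally judged against the Humalog periods, and a large minority of those periods ran under the error. The same exclusion also takes the glucose record of the error out of the analysis. Adverse events are captured by spontaneous report or staff observation (protocol 9.2.1), without active real-time monitoring (protocol 8.3). They are therefore a coarse substitute for sensor data, alarms and glucagon use on those days.

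**Working it through.** The plan gives no adverse-event count or rate, so there is no planned figure to reproduce. Its participant split is consistent: 5 + 7 = 12.

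**Inputs from the documents**

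- Affected sequence n = 5, unaffected n = 7 (SAP 8.1 item 3).
- Each study period 30 days, wash-out 8 days on Humalog (protocol section 3).

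**Assumptions, not in the documents**

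- All 12 Humalog periods were completed, and the wrong settings ran throughout the five affected ones.
- k is the glycaemic event rate on Humalog with Lyumjev settings, divided by the rate on Humalog with Humalog settings.

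**Exposure**

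- Affected Humalog study days: 5 × 30 = 150 of 12 × 30 = 360, or 41.7%.
- Wash-out, if the settings were still in place: up to 5 × 8 = 40 more days, 190 in all.
- If wash-out were counted as Humalog time for all 12, the share would not change: (5 × 38)/(12 × 38) = 190/456 = 41.7%.

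**Effect on a pooled Humalog rate**

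With equal exposure per period, the pooled rate relative to a correctly run Humalog period is (7 × 1 + 5 × k)/12. If the two insulins truly had equal rates, the apparent Lyumjev/Humalog ratio would be the inverse, 12/(7 + 5k).

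| k (assumed) | Pooled Humalog rate multiplied by | Apparent Lyumjev/Humalog ratio when the true ratio is 1 |
|---|---|---|
| 0.5 | 9.5/12 = 0.79 | 1.26 |
| 1 | 12/12 = 1.00 | 1.00 |
| 1.5 | 14.5/12 = 1.21 | 0.83 |
| 2 | 17/12 = 1.42 | 0.71 |
| 3 | 22/12 = 1.83 | 0.55 |

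At k = 2, a true Lyumjev excess of 42% would look like no difference. At k = 0.5 the distortion runs against Lyumjev. A reset part-way through the period would pull every multiplier towards 1.

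**The case against.** The strongest reply is that no adverse-event comparison by insulin is planned. The protocol's only listed safety parameter is side effects of Lyumjev (8.1.2). SAP 5.3.2 speaks of comparing safety parameters between insulins, but every test it lists is on a glucose metric, and item 3 has already removed the affected data from those. Keeping the events is also correct: protocol 9.2.1 records all adverse events and section 10 keeps them even for withdrawals. Dropping them would hide harm. This stands, and it limits the point to a missing label on retained data.

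Three stronger readings are tempting and are not supported:

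- *That harm from the error is counted against Humalog and makes Lyumjev look safer.* No passage assigns these events to Humalog. The SAP says only that regulation was affected, with neither direction nor size. The distortion is nil at k = 1 and reversed below it. Some glycaemic events would also have occurred under correct settings.
- *That 190 patient-days were certainly affected.* This needs five completed periods and wrong settings throughout the wash-out, neither of which is documented.
- *That the record of the error has been withheld.* The data are excluded from analysis, not deleted. SAP 5.1.2 lists the glucose, dosing and alarm data in the AP Portal, and SAP 5.1.1 lists settings adjustments in the CRF. Item 3 openly discloses the error and the number of participants affected.

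Nor would a simple contrast of all 12 Lyumjev exposures with the 7 unaffected Humalog exposures be clean. Those 7 are all first periods, so period and treatment are mixed, and five Lyumjev exposures lose their within-person comparator.

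What the reply does not meet is the inconsistency itself. The safety objective remains, readers will set Lyumjev's events beside Humalog's, and nothing tells them which Humalog events arose under the error.

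**Conclusion.** The point holds as a conditional one. Item 3 retains the adverse events of the Lyumjev-Humalog sequence without marking those that arose under settings the SAP itself says disturbed glucose regulation. If events are read by insulin, up to 41.7% of Humalog study-period exposure is contaminated, given full completion and no reset during the period. The resulting bias in glycaemic event rates cannot be sized or signed from the documents: over k = 0.5 to 3 the pooled Humalog rate is multiplied by 0.79 to 1.83, and Lyumjev is favoured only when k exceeds 1. Events that do not depend on the settings are outside this argument.

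The primary endpoint and Lyumjev's own adverse-event count do not change. Severity is moderate: this affects how the secondary safety objective can be interpreted and whether the effect of the error on participants is reported.

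**What to change.** Amend SAP 8.1 item 3 as follows:

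1. Keep every adverse event. Tabulate by sequence, period, insulin and settings in force, with Humalog use on Lyumjev settings (n=5, including wash-out if the settings were still in place) as a separate column.
2. Give any glycaemic adverse-event comparison between insulins with and without that column. Label it descriptive, because the 7 remaining Humalog periods are all first periods.
3. Summarise the five participants' AP glucose metrics for the affected days descriptively, as safety data and outside the efficacy comparison.
4. State the date on which the settings were reset for each participant, or that it is unknown, and say explicitly whether adverse events are among the data affected by the deviation.

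The cost is SAP wording plus one extra table and one summary from data already held. In the version without the affected column, the Humalog comparator falls from 12 participants to 7.
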